1.33 STATISTICAL ANALYSES

1.33.1 General Approach

Data will be transmitted from the motion sensors to a secure NIH server for storage. Motion data will be quality checked and corrupted waveforms will be removed. Waveforms corresponding to activity (motion artifacts) will also be removed, per standard signal processing techniques. The waveforms will then be parsed out by corresponding volume of inspiration. A customized model will be fine-tuned on these sequences, learning to recognize patterns in chest wall motion associated with each incentive lung volume. To ensure that the model is unbiased, class balancing will be performed for both demographic and clinical labels using majority undersampling techniques. The transformer model will be fine-tuned and validated on the subjects in the dataset. Once the model is fully developed from the data collected in this study, we will test it against the traditional incentive spirometry to calculate its accuracy.

1.33.2 Analysis of the Primary Endpoints

Primary Endpoint: A database of motion waveforms corresponding to each measured volume of inspiration via traditional incentive spirometer.

This endpoint will be deemed successfully completed once the data has been transmitted from the motion sensor to the secure NIH server for all participants. The primary goal of this study is to collect waveform data to correlate changes in chest wall motion with volume of inspiration. The first step in doing so is creation of a database with this information. All motion data will be quality checked and corrupted waveforms will be removed. Waveforms corresponding to activity will also be removed, per standard signal processing techniques.

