1.1 SYNOPSIS

Title:	Feasibility of Measuring Volume of Inspiration Via Non-Invasive Motion Sensors
Study Description:	This protocol is a basic physiologic proof-of-concept study enrolling normal volunteers to determine the feasibility of measuring volume of inspiration from chest wall motion measured via non-invasive thoracic motion sensors. The motion sensors are not medical devices because they are not intended to diagnose a disease or condition or to cure, mitigate, treat or prevent disease. Since motion sensors are not being evaluated for diagnostic purposes or being studied themselves within the context of this protocol and are only intended to collect physiological data, they are not to be considered investigational. The data collected in this feasibility study will not contain any personally identifiable information (PII). In this study, healthy participants will complete a total of approximately 18 measured breaths through a traditional incentive spirometer while wearing small, non-invasive motion sensors on their thorax at approximately the level of the 9 th and 10 th ribs unilaterally or bilaterally. The incentive spirometer is an FDA approved medical device. This study does not aim to study the safety or effectiveness of this device but rather utilize the device as a tool to measure volume of inspiration. The waveform data collected from the devices with each breath will then be analyzed with the intention to develop an algorithm that could convert chest wall motion to a discrete volume of inspiration in real time. Total enrollment time will be about 10-30 minutes per participant.
Objectives:	
Primary:
 
To collect chest wall motion data corresponding to various volumes of inspiration from a non-invasive wearable device.
 
Secondary:
 
To develop an algorithm which can convert chest wall motion to volume of inspiration and assess the algorithm using cross-validation strategy.

Endpoints:	
Primary:
 
A database of motion waveforms corresponding to each measured volume of inspiration via traditional incentive spirometer.
 
Secondary:
 
A cross-validated algorithm that converts chest wall motion to volume of inspiration.

Study Population:	Healthy volunteers of both sex and demographic groups who are ages 18 and older.

Abbreviated Title: Wearable Incentive Spirometry

Version Date: 09/08/2025

[figure not shown]

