1.5 OVERALL DESIGN

Healthy volunteers (n = 30) will be recruited for participation in this proof-of-concept study. Each participant will be consented and assigned a study number to ensure that all data is non-PII. Participants will be asked to fill out a de-identified form with their age, sex, height and weight prior to application of motion sensor (see section **1.6**).

Each participant will wear the devices for approximately 10-30 minutes while they perform a series of breathing exercises. The thoracic wearable will be adhered unilaterally or bilaterally at approximately the level of the 9th and 10th ribs at the mid-axillary line. Hypoallergenic double-sided tape will be used to adhere the motion sensor to the volunteers' torso in this position. The participant will ideally take three breaths through a traditional incentive spirometer while wearing the devices at each of the following volumes: 250mL, 500mL, 1000mL, 1500mL, 2000mL, and 2500mL. Each breath will be held for approximately 5 seconds before being released. Throughout this period, the thoracic wearable will be detecting chest wall expansion. All data will be transmitted to a secure server located within the NIH clinical center for analysis and model creation. Upon completion of the breathing exercises, the device will be removed from the participant, and the participant will be free to leave. There will be no further study visits or contact required.

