1.6 SCIENTIFIC RATIONALE FOR STUDY DESIGN

This is a basic physiologic proof-of-concept study to determine the feasibility of using a motion sensor to indirectly measure volume of inspiration. As such, there is no control group. The study design is appropriate to meet the goals of this study which are to acquire motion data from people taking measured breaths through traditional incentive spirometer.

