1.26 STUDY EVALUATIONS & PROCEDURES

All patients consented for participation will undergo the following procedures:

1. Recording self-reported age, sex, height, and weight.
2. Application of the motion sensor using a medical grade double sided adhesive.
3. While seated, each participant will ideally take three breaths at each of the following volumes through a traditional FDA approved incentive spirometer: 250mL, 500mL, 1000mL, 1500mL, 2000mL, and 2500mL. The participants will hold each breath for approximately 5 seconds before exhaling.
4. Data collection will include motion data transmitted from the motion sensor to a secure NIH server.

Abbreviated Title: Wearable Incentive Spirometry

Version Date: 09/08/2025

None of this data will be transmitted back to the participants themselves. All findings associated with this study will, however, be made publicly available upon the completion of this study.

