1.31 SAMPLE SIZE DETERMINATION

We hope to recruit approximately 30 participants for initial proof-of-concept data collection.

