1.33.5 Sub-Group Analyses

Results will be analyzed as a whole and then based on sex and BMI to determine if these factors significantly impact chest wall motion corresponding to teach volume of inspiration.

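### The feasibility conclusion rests on one fine-tuned transformer; no pre-specified analysis estimates the motion-volume relation or gives a simple benchmark for the transformer's accuracy

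*Combined protocol and SAP*

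**What the plan says.** **Purpose.** Section 1.6 says: "This is a basic physiologic proof-of-concept study to determine the feasibility of using a motion sensor to indirectly measure volume of inspiration". Section 1.33.2 says: "The primary goal of this study is to collect waveform data to correlate changes in chest wall motion with volume of inspiration". The objectives and endpoints table gives the same reason for building the database. The secondary hypothesis in 1.30 is that sensor motion yields inspired volume accurately; no metric or threshold is attached.

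**Planned analyses.**
- 1.33.2: the primary endpoint is met once every participant's data have reached the server.
- 1.33.1: "The transformer model will be fine-tuned and validated on the subjects in the dataset". Accuracy is then to be calculated against the spirometer, with no measure named.
- 1.33.3: pre-trained models are assessed by cross-validation with a held-out test set. The number of folds and the source of the pre-training are not given.
- 1.33.5: "Results will be analyzed as a whole and then based on sex and BMI". This concerns motion at each volume, but no statistic or model is named.
- 1.33.7: exploratory analyses are marked not applicable.

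**Sample.** Section 1.31 consists of one sentence: "We hope to recruit approximately 30 participants for initial proof-of-concept data collection". The synopsis says that "healthy participants will complete a total of approximately 18 measured breaths through a traditional incentive spirometer". Section 1.26 lists the volumes as "250mL, 500mL, 1000mL, 1500mL, 2000mL, and 2500mL", and sections 1.2 and 1.5 agree. Section 1.17.1 adds 750 mL, making seven. Three breaths per volume is an ideal; section 1.7 accepts one attempt at each.

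**The concern.** The data are collected to relate motion to volume, yet no planned analysis would report how much motion changes per unit volume, how closely it tracks volume within a person, or how far that relation differs between people. The transformer's held-out accuracy is the only planned evidence on conversion.

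That leaves either result hard to interpret. Poor accuracy could mean that the sensor carries little information on volume, or that this model could not be adapted on so few people. Good accuracy would not show whether a one-variable regression would have done as well. Section 1.8 makes a larger study under a new protocol depend on this one succeeding and does not define success, so the reading of the result matters.

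**Working it through.** **1. Breath count.** Six volumes x 3 breaths = 18 per person, which reproduces the synopsis figure. With 30 people (1.5, 1.31), 30 x 18 = 540. This is close to a ceiling on the six-volume list:
- One attempt per volume (1.7): 30 x 6 = 180.
- Seven volumes (1.17.1): 7 x 3 = 21 per person and 30 x 21 = 630. This does not match the synopsis, so the lists must be reconciled.
- Artefact removal (1.33.1) lowers any of these by an unstated amount.
- Majority undersampling (1.33.1), if it drops whole participants to balance sex: an assumed 20:10 split leaves 2 x 10 = 20 people and 20 x 18 = 360 breaths; an assumed 24:6 split leaves 12 people and 216 breaths.

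The sample size of 30 cannot itself be reproduced, because no precision or power target is given.

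**2. Data per fitted model.** The number of folds is not stated. Assume five folds of 30/5 = 6 people, with three folds for fitting, one for validation and one for test. Each model is then tuned on 18 people and 18 x 18 = 324 breaths, before any removals.

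**3. What a simple analysis could deliver from the same data.**
- *Within-person correlation.* Fisher-z interval tanh(atanh r ± 1.96/√(df − 1)), with df = N(k − 1) − 1. For N = 30, k = 18, df = 509: an assumed r of 0.5 gives 0.43 to 0.56, and 0.8 gives 0.77 to 0.83. For k = 6, df = 149: 0.37 to 0.61 and 0.73 to 0.85. The formula assumes a common slope; if slopes differ between people, these intervals are too narrow.
- *Mean slope.* Half-width t(29) x CV/√30, between-person component only. An assumed between-person CV of 20%, 30% or 40% gives ±7.5%, ±11.2% or ±14.9%.
- *Individual slopes.* Under the same 20% to 40%, about 95% of people lie within ±1.96 x CV of the mean: ±39% to ±78%. This spread, not the precision of the mean, governs conversion in a new person.

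**4. Can model flexibility alone produce a failing result?** An illustration with assumed values: 60 simulated data sets of 30 people x 18 breaths, one informative feature, between-person log-slope SD 0.3, noise SD 0.2 L, five-fold cross-validation by participant, and essentially unpenalised least squares. Only the number of added noise predictors varies.

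| Predictors | Median cross-validated R² (5th to 95th percentile) |
|---|---|
| 1 | 0.69 (0.58 to 0.80) |
| 50 | 0.66 (0.52 to 0.73) |
| 200 | 0.48 (0.20 to 0.62) |
| 400 | −3.1 (−5.2 to −1.9) |

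The signal is the same in every row. The last row is extreme: 401 coefficients, including the intercept, are fitted to 24 x 18 = 432 breaths. These are not transformer results; pre-training or regularisation would lessen the effect. The table shows only that a poor held-out score need not mean absent signal.

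**The case against.** The strongest reply has four parts.

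- *The primary goal is collection.* Section 1.33.2 calls the database the first step, and its endpoint is met on data transfer. A reader might infer that the primary endpoint is at risk from a poor model. The documents do not support that: it cannot fail through model fit. This part stands, and confines the point to the secondary endpoint and the feasibility conclusion.
- *The model is fine-tuned from a pre-trained one.* A reader might infer that a transformer must fail on 540 breaths. Nothing in the documents shows this, and pre-training weakens the small-sample argument. It does not supply a benchmark, and its source is unstated.
- *The harm is inferred.* No section says that a poor fit will be read as infeasibility. The waveforms are archived (1.36, 1.37), so a simple analysis could follow a poor result. It is therefore too strong to say that the study could not answer its question. An analysis chosen after seeing the transformer fail would, however, carry less weight.
- *A single-feature model has the same weakness.* The sensor reports several three-axis signals (1.9.1), and placement may be on one side or both (1.5). One angle change may miss non-linear or multi-axis information. This stands against making the simple model the decision rule, but not against reporting it.

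**Conclusion.** The point holds as a gap in the analysis of the secondary endpoint. The only planned evidence that motion can be converted to volume is the accuracy of one model class. It would be tuned on at most about 540 breaths from 30 people on the six-volume list, and fewer after removals and balancing. No pre-specified analysis estimates the underlying relation or gives a reference level for that accuracy.

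The breath counts follow from the documents. The fold layout, sex splits, correlations and slope CVs are assumptions. A reader might take the ±7.5% to ±14.9% as showing that conversion is feasible, but it describes only the mean slope; the matching individual spread is ±39% to ±78%. The planned data suit a simple analysis of the relation, and its answer on feasibility could go either way.

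This is an inexpensive improvement worth making before the analysis starts. It does not invalidate the design.

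**What to change.** In section 1.33.3:
1. Define one motion-amplitude summary per breath, for example the change in sensor angle from start of breath to end of inspiration. State the axis and the rule for one-sided and two-sided placement.
2. Fit a linear mixed model of amplitude on volume with random intercept and slope by participant. Report the slope with 95% CI, the residual SD and the between-person slope SD.
3. Score a low-dimensional regression predicting volume from amplitude on the same held-out participants and with the same error metric as the transformer. This requires folds formed by participant and a named metric.
4. Report the two side by side, and state that the simple model is a benchmark for interpreting the transformer and not the sole feasibility rule. A good benchmark with a poor transformer points to the model. A transformer no better than the benchmark gives no case for the added complexity. A poor benchmark alone does not show infeasibility.

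Separately, reconcile the seven-volume list in 1.17.1 with the six-volume lists in 1.2, 1.5 and 1.26, so that the number of breaths is fixed.

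The cost is about a day of analysis on data already being collected, plus SAP wording, with no added burden on participants.

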1.33.3 Analysis of the Secondary Endpoint(s)

Secondary Endpoint: A cross-validated algorithm that converts chest wall motion to volume of inspiration.

Motion waveforms will be annotated by volume of inspiration. A model will be fine-tuned on these sequences, learning to recognize subtle deteriorations in the waveform that correspond with varying volumes of inspiration. The pre-trained AI models will be validated for each task (e.g., each measured volume of inspiration). This will be done using a validation set and then test using a held-out test set wherein no parameter optimization is performed. Different validation and test sets will be generated using a cross-validation strategy such as stratified K-fold.

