1.4.3 Assessment of Potential Risks and Benefits

The potential knowledge that may result from this study is considerable and may balance any potential risks to the participants. Proving that it is possible to detect volume of inspiration and respiratory rate from a non-invasive, wearable motion sensor could inform future studies which might work to improve IS compliance, data transmission, longitudinal tracking, and nursing burden.

OBJECTIVES AND ENDPOINTS

OBJECTIVES	ENDPOINTS	JUSTIFICATION FOR ENDPOINTS
Primary		
To collect chest wall motion data corresponding to various volumes of inspiration from a non-invasive wearable device.	A database of motion waveforms corresponding to each measured volume of inspiration via traditional incentive spirometer.	The primary goal of this study is to collect data to correlate changes in chest wall motion with volume of inspiration. The first step in doing so is the creation of a database with this information.
Secondary		
To develop an algorithm which can convert chest wall motion to volume of inspiration and assess the algorithm using cross-validation strategy.	A cross-validated algorithm that converts chest wall motion to volume of inspiration.	This endpoint will allow us to prove the ability to calculate volume of inspiration from chest wall motion and assess its accuracy.

STUDY DESIGN

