1.8 END-OF-STUDY DEFINITION

A participant is considered to have completed the study if he or she has completed the demographic form and attempted all volumes of inspiration with the motion sensor in place.

Should the results of this basic physiologic proof-of-concept study be successful, future analysis of the technology developed (algorithm) would be submitted under a new IDE protocol to perform a study on a larger scale using this device and the algorithm which would be developed and marketed to assist in diagnosis, likely be considered a medical device at that time beholden to 21 CFR 812, used off label and likely would be NSR along with the algorithm that is developed.

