1.30 STATISTICAL HYPOTHESIS

- Primary Endpoint Hypothesis: We will be able to transmit waveform data corresponding to each breathing exercise from the wearable motion sensor to the secure NIH database.
- Secondary Endpoint Hypothesis: Chest wall motion harnessed by a wearable motion sensor can be accurately converted to volume of inspiration.

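### The secondary endpoint is the delivery of an algorithm, with no error measure, interval or no-skill reference to support the claim that volume can be calculated accurately

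*Combined protocol and SAP*

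**What the plan says.** The Synopsis (1.1), the Objectives and Endpoints table and section 1.33.3 all word the secondary endpoint the same way: "A cross-validated algorithm that converts chest wall motion to volume of inspiration".

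Three other places attach a stronger meaning to it:

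- The table's justification column: "This endpoint will allow us to prove the ability to calculate volume of inspiration from chest wall motion and assess its accuracy".
- The secondary hypothesis in 1.30: "Chest wall motion harnessed by a wearable motion sensor can be accurately converted to volume of inspiration".
- Section 1.8, which looks ahead to a larger study under a new IDE protocol: "Should the results of this basic physiologic proof-of-concept study be successful".

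On evaluation, 1.33.1 says of the finished model that "we will test it against the traditional incentive spirometry to calculate its accuracy". Section 1.33.3 plans a held-out test set on which nothing is tuned, and adds: "Different validation and test sets will be generated using a cross-validation strategy such as stratified K-fold".

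The primary endpoint has a completion rule in 1.33.2: "This endpoint will be deemed successfully completed once the data has been transmitted from the motion sensor to the secure NIH server for all participants". Section 1.33.3 has no counterpart. Section 1.31 gives about 30 participants, with no precision or accuracy target.

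**The concern.** An endpoint worded as a product is reached once the product exists. Any model that has been run through folds is a cross-validated algorithm, whether its predictions are good or useless. The words *prove*, *accurately* and *successful* then have no stated link to a result.

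This matters because the primary hypothesis in 1.30 concerns data transmission only. The question in the study's title, whether inspired volume can be measured from chest motion, is answered only by the secondary endpoint. If the reading of that endpoint is settled after the results are known, the same number could be presented as support or as failure.

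Naming an error metric would not be enough. An error in mL still needs something to be judged against, and a percentage correct can look high or low depending only on how the task was set up.

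**Working it through.** **The plan's own figures.** There is no design figure to reproduce: no accuracy target, margin, alpha or power is stated. The breath count does reproduce. The six volumes in 1.2, 1.5 and 1.26 with three breaths each give 6 × 3 = 18 per participant, as in the Synopsis, and 30 × 18 = 540 in all. Section 1.17.1 adds 750 mL, which would give 7 × 3 = 21 and 630.

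**Accuracy of a model with no skill, equal frequencies.** Section 1.33.3 validates each volume as a task; 1.33.1 plans class balancing but does not say whether it applies to volume or to the test data. Three framings are therefore open:

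| Framing | No-skill rule | Six volumes | Seven volumes |
|---|---|---|---|
| One choice among all volumes | guess | 1/6 = 17% | 1/7 = 14% |
| Each volume against the rest, balanced | guess | 1/2 = 50% | 1/2 = 50% |
| Each volume against the rest, unbalanced | always answer no | 5/6 = 83% | 6/7 = 86% |

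**Error in mL of a constant prediction.** The mean absolute error (MAE) is smallest when the constant is a median of the target volumes.

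- Six volumes (250, 500, 1000, 1500, 2000, 2500), constant 1250: (1000 + 750 + 250 + 250 + 750 + 1250)/6 = 4250/6 = 708 mL. Any constant from 1000 to 1500 gives the same value.
- Seven volumes, constant 1000: (750 + 500 + 250 + 0 + 500 + 1000 + 1500)/7 = 4500/7 = 643 mL.
- For root mean squared error the best constant is the mean. With six volumes that is 7750/6 = 1292 mL, with error 796 mL; with seven it is 8500/7 = 1214 mL, with error 761 mL.

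All these values assume equal numbers of breaths at each volume. Section 1.7 expects that some participants will not reach the largest volume, and 1.33.1 removes waveforms and undersamples. The true reference will therefore differ and has to be computed on the data actually tested.

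**Why the participant is the unit.** Breaths from one person are likely to be correlated. Take an illustrative 80% accuracy over 540 breaths. Treated as independent, the 95% half-width is 1.96 × √(0.8 × 0.2/540) = 3.4 points. The design effect is 1 + 17 × ICC, where ICC is the within-person correlation. An assumed ICC of 0.1 gives 2.7 and a half-width of 3.4 × √2.7 = 5.5 points; 0.5 gives 9.5 and 10.4 points. The documents give no ICC.

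**Precision of a participant-level MAE.** The half-width with 30 people is t(29) × SD/√30, with t(29) = 2.045. For an assumed between-person SD of 100 to 150 mL this is 37 to 56 mL. The documents give no such SD, so this is an illustration and not evidence that any particular tolerance can be tested.

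**The case against.** The best defence is that this is a single-visit, uncontrolled proof-of-concept study in healthy volunteers, whose primary endpoint is the database. Accuracy against the spirometer will be calculated, a held-out test set is protected from tuning, and a poor result would be visible. A formal pass/fail test is not essential at this stage. All of that stands, and it lowers the severity.

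It also rules out some stronger readings:

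- A reader might infer that the hypothesis in 1.30 cannot fail and that what follows is independent of the data. The documents do not support this. *Accurately* is undefined, which makes the hypothesis vague rather than untestable, and performance will be measured.
- A reader might take 1.8 as a go/no-go rule. It is a forward-looking remark about a possible later protocol and triggers nothing.
- A reader might derive a tolerance from the volume grid, such as 250 mL, half of the 500 mL step in the upper range. No tolerance in the documents supports it. At the lowest volume it is a 100% error. A model that only tells apart the pairs 250/500, 1000/1500 and 2000/2500 and outputs each midpoint has MAE (2 × 125 + 4 × 250)/6 = 208 mL. With the 37 mL half-width above, its upper limit would be 245 mL, so it would pass.

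What the defence does not answer is how the calculated accuracy is to be read. The protocol itself chose the language of proof and supplies no reference for it.

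**Conclusion.** The point holds as a should-fix. On its literal wording the secondary endpoint is met by any cross-validated algorithm, and the plan gives no metric, interval, no-skill reference or criterion that would let the result support the claim of proof or of accurate conversion.

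The size of the ambiguity is large. The same absence of skill reads as 17%, 50% or 83% accuracy with six equally frequent volumes, according to the framing. In mL, no skill corresponds to an MAE of about 708 (six volumes) or 643 (seven). These figures rest on equal representation of the volumes and would move with unreached volumes, removed waveforms and undersampling.

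The finding concerns the interpretation of the secondary endpoint. It does not say that evaluation is missing, and it leaves the primary endpoint unaffected.

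**What to change.** 1. In 1.33.3, restate the endpoint as held-out MAE in mL, computed for each participant and then averaged. Use folds that keep all of a participant's breaths together. Give a 95% confidence interval with the participant as the unit (t interval or participant bootstrap), noting that it is approximate because the fold models share training data.
2. Report beside it the MAE of a constant predictor, set from the training folds and scored on the same test folds. Do not hard-code 708 or 643 mL. The six-volume and seven-volume lists (1.2, 1.5 and 1.26 against 1.17.1) must be reconciled.
3. State that 1.30 is supported, at minimum, only if the model's error is clearly below that reference; for example, the 95% interval for the per-participant difference, model minus constant, lies wholly below zero. Beating the constant shows some skill, not accuracy.
4. If the sponsor wishes to claim accurate conversion in 1.30 or success in 1.8, it should fix and justify its own mL tolerance before modelling begins. Otherwise, replace the proof and accuracy language in the Objectives and Endpoints table and in 1.30 with estimation wording.

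The cost is a few sentences of protocol text and a few lines of analysis, with no extra participants or procedures. The downside is that the study can then fail its secondary hypothesis. The change is worth most if made before any model is fitted.
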